5.4.2. Estimands

Not applicable.

5.4.3. Analysis Methods

Unless otherwise specified, participants will be analyzed according to the vaccination regimen they actually received (i.e. not according to the planned vaccination regimen). Participants who receive Ad26.COV2.S 2.5×10^{10} vp per 0.5 mL will be analyzed together with those who received Ad26.COV2.S 2.5×10^{10} vp per 0.25 mL. Those who receive a 2-active dose regimen will be analyzed in the 2-active dose regimen at the dose level of the 1st active dose actually received.

Safety and Reactogenicity Endpoints

No formal statistical testing of safety data is planned. Safety data will be analyzed descriptively by phase. Selected tables will also be presented by subgroups (age group, sex, SARS-CoV-2 serostatus at baseline [or in seronegative subgroup only if there are less than 5% of seropositive subjects], BMI group, race and ethnicity), as defined in Section 5.8.5. In addition, for selected tables, tabulations pooled by vaccination dose will also be provided. Details are provided in Section 5.6 and Section 5.7.1.

The rate of occurrence of specific local and systemic adverse events will be used to identify the maximum dose with acceptable reactogenicity compared to the rate observed in young-adult participants of study COV3001. Details are provided in Section 5.9.1.

Humoral Immune Response Endpoints

The immunogenicity analyses will be performed on the PPI population.

Immunogenicity results will be presented by vaccination schedule, by SARS-CoV-2 by serostatus at baseline [or in seronegative subgroup only if there are less than 5% of seropositive subjects], and overall, per scheduled time point using the pre-defined visit windows. Selected immunogenicity analyses will also be done on the FAS (participants who became infected during the study will be analyzed as a subgroup and will be shown in the graphs using different colors and symbols) and on key other subgroups (sex, age group and also on BMI, race and ethnicity for the primary endpoint) as defined in Section 5.8.5. Samples taken outside of the allowed window (included in the FAS analysis and excluded from the output in the analysis on PPI) will be included and flagged in the listings as results not included in the PPI analyses.

Categorical variables will be summarized with a frequency table showing counts and percentages. Continuous variables will be summarized using the following statistics, as appropriate: Number of observations, geometric mean, arithmetic mean (mean), 95% confidence interval (CI) for the mean, standard deviation (SD), standard error (SE), median, quartiles (Q1 and Q3), minimum and maximum. Binary variables will be summarized using the following statistics: number of observations, percentages, and Exact Clopper-Pearson 95% CIs (where appropriate).

Data listings, participant profiles and/or participant narratives may be provided as appropriate.

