7. DISCONTINUATION OF STUDY VACCINATION AND PARTICIPANT DISCONTINUATION/WITHDRAWAL

7.1. Discontinuation of Study Vaccination

Study vaccinations will be withheld for the reasons listed below. These participants must not receive any further doses of study vaccine but should remain on study for follow-up of safety and immunogenicity as indicated in the Schedule of Activities (Section 1.3). Additional unscheduled visits may be performed for safety/reactogenicity reasons, if needed. In case of questions, the investigator is encouraged to contact the sponsor.

- Any related AE, worsening of health status or intercurrent illnesses that, in the opinion of the investigator, requires discontinuation from study vaccine
- The participant becomes pregnant
- Unblinding (other than scheduled unblinding) on the participant level that, in the opinion of the sponsor, would compromise the integrity of the data
- Anaphylactic reaction following vaccination, not attributable to causes other than vaccination

- SAE or other potentially life-threatening (Grade 4) event that is determined to be related to study vaccine
- Chronic (>14 days) or recurrent use of systemic corticosteroids and administration of antineoplastic and immunomodulating agents or radiotherapy
- Withdrawal of consent/assent to receive further study vaccination (second vaccination of the 2-dose regimen)
- Participant receives any experimental medication (including experimental vaccines other than the study vaccine) or receives an anti-COVID-19 vaccine or treatment
- Participant previously experienced TTS or heparin-induced thrombocytopenia (HIT), GBS or MIS-C.
- Per the implementation of Amendment 1, the participant has a history of CLS.

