Since CTP amendment 2, the study starts with a Dose Selection Cohort (Part1), where the participants will be randomly assigned in a 1:1:1:1:1:1 ratio to 1 of 3 study arms to receive one active vaccination of Ad26.COV.2 (either 2.5×10^{10} vp per 0.25 mL dose volume, 1.25×10^{10} vp, or 0.625×10^{10} vp) followed by placebo in a 1-(active) dose regimen (Groups 1, 2 and 3, respectively), or 1 of 3 study arms to receive the same dose level of 2.5×10^{10} vp (per 0.5 mL dose volume), 1.25×10^{10} vp, or 0.625×10^{10} vp in a 2-(active) dose (56-day interval) regimen (Groups 4, 5 and 6, respectively). Each study group will contain approximately 50 participants. Since CTP amendment 3, approximately 70% will be 12 to 15 years of age and approximately 30%, 16 to 17 years of age. Adolescents will be unblinded to the primary vaccination regimen at 6 months after the first vaccination. Also, participants in Groups 1-3 will be given a booster vaccination as of 6 months after the last vaccination with active vaccine. The booster dose level will be 2.5×10^{10} vp per 0.5 mL. Participants in Groups 4-6 will be not given a booster vaccination in the study.

The vaccination schedule for Part 1 is displayed in [Table 1](#).

As a part of the COVID-19 program safety oversight, the IDMC will review the data on an ongoing basis, in addition to two study-specific predefined IDMC analyses.

Table 1: Part 1 Vaccination Schedules (Dose Selection Cohort)

Group	N^{a,b,c}	Vac 1	Vac 2	Vac 3
		Day 1	Day 57	Day 184
1	50	2.5×10^{10} vp (0.25 mL)	Placebo	2.5×10^{10} vp (0.5 mL)
2	50	1.25×10^{10} vp	Placebo	2.5×10^{10} vp (0.5 mL)
3	50	0.625×10^{10} vp	Placebo	2.5×10^{10} vp (0.5 mL)
4	50	2.5×10^{10} vp (0.5 mL)	2.5×10^{10} vp (0.5 mL)	none
5	50	1.25×10^{10} vp	1.25×10^{10} vp	none
6	50	0.625×10^{10} vp	0.625×10^{10} vp	none

N = number of participants; n/a = not applicable; SDL = selected dose level; Vac = vaccination; vp = virus particles.

a Not more than 70% of males or females should be randomized in each age group

b All participants must be seronegative for SARS-CoV-2 antibodies at baseline.

c Approximately 30% of participants should be between 16 to 17 years age and approximately 70% should be between 12 to 15 years of age.

Not more than 70% males or females will be randomized in each age group. The randomization will be stratified by sex and age group. In Part 1, screening will aim to ensure participants are seronegative at baseline for SARS-CoV-2 antibodies.

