3. SAMPLE SIZE DETERMINATION

The sample size for Part 1 shall enable selection of appropriate doses and regimens. Decision making on the optimal regimen will primarily take into account safety and reactogenicity data. Non-binding guidelines on dose and regimen selection are described in Section 5.9.1.

Additionally, any available immunogenicity data from Part 1 participants and data from other Janssen clinical trials of Ad26.COV2.S will also be considered.

With a sample size of 50 participants per study group, the width of the 90% CI for the observed proportion of adverse events will vary between 5.8% and 24.8% depending on the observed proportion. Assuming pooling of adverse event data after the first active dose on the same dose level of the 1- and 2-dose regimen, the width of this confidence interval will vary between 3% and 17.3% depending on the observed proportion ([Table 2](#)).

Table 2: 90% Two-Sided CI for Possible Observed Rate of Adverse Events

Observed Rate	0%	5%	10%	25%	50%
50 Participants	(0, 5.8%)	(1.2%, 13.4%)	(4%, 19.9%)	(15.3%, 37%)	(37.6%, 62.4%)
100 Participants	(0, 3%)	(2%, 10.2%)	(5.5%, 16.4%)	(18%, 33.1%)	(41.4%, 58.6%)

In Part 1, a target of approximately 300 adolescents, seronegative for SARS-CoV-2 antibodies at baseline will be enrolled.

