5. STATISTICAL ANALYSES

5.1. General Considerations

Details of the vaccine schedules associated to the primary vaccine regimen will be provided in the data presentation specification (DPS) document. Vaccination schedule have 2 components:

- Primary Vaccine Regimen (1-active dose or 2-active dose)
- Booster Vaccination (i.e. after unblinding)

Unless specified otherwise, analyses outputs will be produced by age group (12 to 15, 16 to 17, and overall). Where applicable, output will include results by dose level (1-active dose regimen and 2-active dose regimen combined) to report the post-dose 1 period.

All safety and immunogenicity data after a participant has received any other SARS-CoV-2 vaccine not part of the protocol will not be tabulated. Those data will be in listings.

A baseline (or reference) value will be defined as the value of the last available assessment prior to the first vaccination on Day 1, unless specified otherwise.

Unless otherwise stated, safety analyses will be conducted on the FAS, Immunogenicity analyses on the PPI.

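### Read plainly, the as-received rule in SAP 5.4.3 moves Group 4-6 participants whose second dose is withheld into the 1-active-dose column, which can make the 2-dose regimen look safer in some safety tables

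*SAP*

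**What the plan says.** SAP 5.4.3 (Analysis Methods) states that, unless otherwise specified, "participants will be analyzed according to the vaccination regimen they actually received (i.e. not according to the planned vaccination regimen". It pools recipients of 2.5×10^10 vp in 0.5 mL with recipients of the same dose in 0.25 mL. It then adds, with the dose level taken as given and not as planned: "Those who receive a 2-active dose regimen will be analyzed in the 2-active dose regimen at the dose level of the 1st active dose".

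SAP 5.1 lists the available categories as "Primary Vaccine Regimen (1-active dose or 2-active dose". Placebo defines no category of its own.

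Under SAP 1.2, "participants will be randomly assigned in a 1:1:1:1:1:1 ratio". Groups 1-3 receive active vaccine and then placebo, and Groups 4-6 receive active vaccine twice.

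Protocol 7.1 withholds further doses for several reasons. One is "Any related AE, worsening of health status or intercurrent illnesses that, in the opinion of the investigator, requires discontinuation from study vaccine". Others are anaphylaxis and an SAE or Grade 4 event related to vaccine. Such participants stay on study for follow-up. They remain in the Full Analysis Set, which needs one documented vaccination (SAP 4), and under Protocol 6.3 they are not replaced.

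SAP 5.1 and 5.1.6 also plan post-dose-1 output pooled by dose level across the two regimens, in addition to the separate group analyses. SAP Table 4 defines cumulative safety intervals: Up to Day 85, Primary Vaccination Period and Entire Study.

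**The concern.** Whether a participant receives dose 2 is known only after randomization, and in some cases it depends on what happened after dose 1. A rule that assigns the column by doses received can therefore sort participants on the safety outcome being tabulated. The effect is not symmetric. A Group 4-6 participant stopped after dose 1 has had one active dose and fits the 1-active-dose category. A Group 1-3 participant who misses placebo has also had one active dose and is already in that category.

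MAAEs, SAEs and AESIs are primary safety endpoints that run from the first vaccination to 6 months after the last dose or to the end of the study (SAP 5.4.1). In those summaries, a first-dose event that stopped the regimen would be counted against the 1-dose regimen although the participant was randomized to two doses. SAP 3 says that the choice of regimen rests primarily on safety and reactogenicity, so a reader will compare these columns even though no test is planned.

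**Working it through.** **1. Where does a participant with only dose 1 go?** The rule is by regimen received (5.4.3), and the categories are 1-active and 2-active (5.1). Only those who receive a 2-active-dose regimen are placed in the 2-active column (5.4.3). One active dose therefore leads to the 1-active column. SAP Table 3 foresees such participants, since its long-term follow-up phase has a branch for a single administered dose, but no sentence assigns them a column.

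**2. Which outputs are exposed?**
- *Exposed:* by-schedule post-dose-1 columns, follow-up phases, and the three cumulative intervals of Table 4 named above.
- *Not exposed:* post-dose-1 tables pooled by dose level, because a move within the pool changes nothing.
- *Not exposed:* post-dose-2 period tables. Table 3 starts that period at the second vaccination, so someone without dose 2 never enters it.
- *Immunogenicity:* Crit23 in SAP 6.3 drops samples later than Day 57 + 8 when there is no second vaccination. Only the Day 1, 29 and 57 samples could change column.

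**3. The plan's own precision figure.** SAP 3 begins: "With a sample size of 50 participants per study group, the width of the 90% CI for the observed proportion of adverse events". It gives a range of 5.8% to 24.8%, or 3% to 17.3% with 100 participants. Exact Clopper-Pearson 90% two-sided intervals reproduce every cell of SAP Table 2. Examples with 50 participants are 0% (0, 5.8%), 10% (4.0%, 19.9%) and 50% (37.6%, 62.4%). The widest interval is 24.8 points with 50 and 17.3 points with 100.

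**4. Size of the shift.** Take n = 50 per column and x first-dose events in each column, so the true rates are equal. Suppose m participants move from the 2-dose to the 1-dose column, and k of them had the event.

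- 2-dose column: (x − k)/(n − m)
- 1-dose column: (x + k)/(n + m)
- Gap (1-dose minus 2-dose): 2(kn − xm)/(n² − m²)

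The gap favours the 2-dose regimen only if k/m exceeds x/n, that is, if movers have the event more often than participants overall.

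*An event that mandates stopping* (x = 1, m = k = 1): 1/50 v 1/50 becomes 0/49 = 0% v 2/51 = 3.9%. The 90% exact intervals are (0, 5.9%) and (0.7%, 11.8%).

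*At 20%*, the Grade 3 rate that SAP 5.9.1 assumes for the comparator (x = 10), with every mover having had the event:

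| m | 2-dose | 1-dose | Gap (points) |
|---|---|---|---|
| 0 | 10/50 = 20.0% | 10/50 = 20.0% | 0 |
| 1 | 9/49 = 18.4% | 11/51 = 21.6% | 3.2 |
| 2 | 8/48 = 16.7% | 12/52 = 23.1% | 6.4 |
| 3 | 7/47 = 14.9% | 13/53 = 24.5% | 9.6 |

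The pooled rate is 20/100 = 20.0% in every row.

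*A mover without the event* (m = 1, k = 0, x = 10), for example after withdrawal of consent: 10/49 = 20.4% v 10/51 = 19.6%. This is 0.8 points the other way.

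The values of m and k are assumptions, since the documents give neither.

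**5. With the randomized column kept,** the shift is zero by construction: 10/50 v 10/50, or 1/50 v 1/50.

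**The case against.** The SAP never states that such a participant moves. SAP 1.2 describes the 1-dose regimen as active vaccine followed by placebo, so someone with a single injection has completed neither regimen. The rule is qualified by its opening words, and details of the schedules are left to the data presentation specifications. The sentence on the first active dose can be read as a rule for dosing errors. This stands as a limit: the placement is the plain reading of the text and not an explicit instruction. It does not remove the point, because the stated rule rejects the planned regimen and offers no third category.

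A reader might infer that the plan's main safety comparison of one against two doses is biased and that regimen selection is compromised. The documents do not support that. Between-group comparison is described for immunogenicity (Protocol 9.1), while safety is summarized descriptively. The only specified reactogenicity benchmark is young adults from other studies, and SAP 5.9.1 says that those guidelines will not be assessed in this study. Pooled tables already cover the first dose.

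A reader might also infer a large distortion. A Grade 3 event alone does not stop dose 2 under Protocol 7.1. Protocol 9.2.2 does not anticipate AEs that preclude further vaccination. Some reasons for stopping, such as pregnancy, withdrawn consent or another COVID-19 vaccine, are not first-dose reactions. Movers would also be visible in part, since SAP 5.2 tabulates and lists discontinued vaccination and SAP 5.7.1.3 provides listings or narratives for SAEs and AESIs. All of this stands, and it lowers the severity.

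**Conclusion.** The concern holds for by-schedule post-dose-1 columns, follow-up phases and cumulative MAAE, SAE and AESI summaries. In these, the rule as written can move first-dose events that stopped vaccination from the 2-dose to the 1-dose column, and no Group 1-3 participant moves in return.

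The size is unknown. With about 50 per group, one affected mover makes a gap of roughly 3 to 4 points, well within the interval widths the plan accepts. Several movers at one dose level would be needed for a gap near 10 points. For a rare serious event, one mover is enough to empty one column and double the count in the other.

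The conclusion rests on three assumptions: the plain reading of 5.4.3, no contrary rule in the unseen specifications, and movers who have the event more often than participants overall. Severity is moderate or minor. No formal test or decision rule is affected.

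**What to change.** In SAP 5.4.3, state that the as-received rule applies to errors in product or dose level at an injection. Add that a missed or withheld second dose does not change the randomized 1-active or 2-active column. List participants who missed dose 2, with the reason, by randomized group. Show the as-received regimen as a sensitivity table.

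Handling of dosing errors and the pooled dose-level tables stay as planned. The cost is wording, one change to the derivation of the treatment variable, and minor reprogramming. No new data are needed. SAP version 5.0 follows the primary analysis, so the final tables may differ slightly from those already produced, and a footnote should explain any difference.

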2. STATISTICAL HYPOTHESES

There is no formal hypothesis testing in Part 1.

Descriptive statistics will be reported to descriptively compare vaccine immunogenicity in adolescents from this study VAC31518COV3006 versus vaccine immunogenicity in selected young adults (18 to 25 years of age) from study VAC31518COV3001 or study VAC31518COV3009 (with similar baseline characteristics to the participants expected to be enrolled in this study – see Section 6.11), and between study groups in VAC31518COV3006.

All enrolled participants were seronegative for SARS-CoV-2 antibodies when screened with local rapid finger-prick serology testing at baseline. However, the primary analysis results have shown that many participants were retrospectively established to be SARS-CoV-2 seropositive at baseline by central testing with Nucleocapsid (N) and/or Spike (S) -based serology. Therefore data from SARS-CoV-2 seropositive young adult (18 to 25 years of age) selected from other Phase 3 studies will be used to compare vaccine immunogenicity in seropositive at baseline adolescents from this study.

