4. POPULATIONS (ANALYSIS SETS) FOR ANALYSIS

Analysis Sets	Description
Enrolled	All participants who sign the main ICF.
Randomized	The randomized analysis set includes all participants who were randomized in the study.
Full Analysis Set (FAS)	The Full Analysis Set will include all participants with at least one vaccine administration documented.

Analysis Sets	Description
Per Protocol Immunogenicity Set (PPI) ^a	The Per Protocol Immunogenicity population will include all randomized and vaccinated participants for whom immunogenicity data are available excluding data from participants with major protocol deviations expected to impact the immunogenicity outcomes (see details in Section 6.3). In addition, samples obtained after missed vaccinations, samples obtained from participants after SARS-CoV-2 infection (if confirmed by molecular testing or non-S-ELISA [or equivalent assay]), occurring during the study after randomization (if applicable), after other SARS-CoV-2 vaccination outside the study, and samples obtained outside pre-defined time windows will be excluded from the analysis set (see details in Sections 5.1.4 and 6.3).

^a If a participant is vaccinated out of window due to a study pause, this will not by default be a reason for excluding this participant from the PPI. Participants who were seronegative by local serology finger-prick test on Day 1 prior to study entry but were determined to be seropositive at baseline by central N- or S- serology testing will also be included (as the results from those assessments are not known prior to randomization).

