5.1.6. Analyses by Groups and Pooled Across Groups

In Part 1, summary outputs will be produced with pooled study groups that received the same dose up to D57 in addition to the analyses planned for each study group separately, unless specifically indicated otherwise. Immunogenicity analyses will be carried out by SARS-CoV-2 serostatus at baseline (in participants with a baseline result by central N- and S- serology testing, in PPI or FAS) and 'overall' (all participants, in PPI or FAS).

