5.8.1.4. Immunogenicity Against the Insert

5.8.1.4.1. Humoral assays

The seroresponse rate of S-ELISA (or equivalent assay, e.g. MSD), and the VNA will be reported as the proportion of participants with either:

- a baseline sample value of less than or equal to the lower limit of quantitation (LLOQ; [\leq LLOQ]) and a postbaseline sample strictly greater than the LLOQ ($>$ LLOQ), or
- a baseline sample value strictly greater than the LLOQ ($>$ LLOQ) and a postbaseline sample value representing an at least 4-fold (\geq 4-fold) increase from the baseline sample value.

In addition, the following definition of seroresponse rate of the VNA (and possibly S-ELISA or equivalent assay e.g. MSD) will be reported as an exploratory endpoint: the proportion of participants with at least 4-fold increase from the baseline sample value, where a baseline sample value of less than or equal to the lower limit of quantitation will be set to LLOQ for the analysis.

For S-ELISA and VNA (both wild-type virus and pseudovirion expressing S protein, as available) assays, the following results will be calculated: N, geometric mean and corresponding 95% CI of

the actual values and fold increases from baseline and from pre-dose 2 or pre-dose 3 (for time points after dose 2 and time points post booster, respectively) will be tabulated and graphically presented.

For the calculation of the geometric mean and its corresponding 95% CI, the arithmetic mean and its corresponding 95% CI are calculated on the \log_{10} transformed values. These values are back transformed to provide the geometric mean and its corresponding 95% CI.

Actual values are tabulated and shown as dot plots with dots for participant values, and the corresponding geometric mean and 95% CI per time point for each assay. In addition, GMT (VNA) or GMC (S-ELISA or equivalent assay, e.g. MSD) plots over time, combining the regimens in one graph (without individual participant dots) will also be generated.

Participant profiles of the actual values over time will be graphically presented. In the graphs, original values will be displayed on the \log_{10} scale. Reverse distribution curves of the actual values will be provided for selected time points. Further details and/or updated rules will be provided in the DPS.

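### The overall GMC/GMT of each group is an unweighted mix of seropositive and seronegative participants, so it carries avoidable chance noise from that group's own seropositive share

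*SAP*

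**What the plan says.** - **Presentation.** SAP 5.1.6: "Immunogenicity analyses will be carried out by SARS-CoV-2 serostatus at baseline" and also overall, where overall means "all participants, in PPI or FAS". SAP 5.4.3 repeats this for the primary humoral endpoint: by schedule, by serostatus "and overall, per scheduled time point using the pre-defined visit windows".
- **Method.** For the geometric mean and its CI, SAP 5.8.1.4.1 says that "the arithmetic mean and its corresponding 95% CI are calculated on" the log10 values and then back-transformed. No weighting, covariate or standardisation is given, and SAP 5.4.2 marks estimands as not applicable.
- **Who is in the set.** Under SAP 4, participants who passed the finger-prick test but were "determined to be seropositive at baseline by central N- or S- serology testing will also be included" in the PPI.
- **How common this is.** SAP 2 reports that "many participants were retrospectively established to be SARS-CoV-2 seropositive at baseline by central testing". No percentage is given.
- **Allocation.** SAP 1.2: "The randomization will be stratified by sex and age group". Also: "Each study group will contain approximately 50 participants".
- **Importance of serostatus.** SAP 6.11 puts baseline serostatus first among the characteristics expected to separate immune responses when it selects matching young adults.

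Neither document says whether the overall or the by-serostatus result is the main reading of the primary immunogenicity endpoint.

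**The concern.** SAP 2 makes descriptive comparison between study groups a stated aim. With no hypothesis test, readers will rely on point estimates and intervals. In the overall column, a group that happens to contain more seropositive participants shows a higher geometric mean at the same dose effect. A chance difference in share could therefore separate two equal doses on the page, or mask a real difference between adjacent doses. The plan puts serostatus first in its external comparison with young adults but makes no allowance for it in the overall comparison of its own randomised groups.

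**Working it through.** **The plan's own precision figure.** The only one is for adverse-event proportions (SAP 3, Table 2): 90% CI widths of 5.8% to 24.8% at n=50. These reproduce as Clopper-Pearson intervals; at zero events, for example, 1 − 0.05^(1/50) = 5.8%. Nothing is stated for GMCs.

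**Inputs.** n = 50 per group is from SAP 1.2. The rest are assumptions, because the documents do not give them: within-stratum SD s = 0.45 log10; seropositive share p = 20% to 60%; gap g between stratum means = 0.5 to 1.5 log10. The central case is p = 40%, g = 1 (10-fold).

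**Step 1: what the overall GMC is.** log10(overall GMC) = log10(GMC seronegative) + p × g. Two groups with identical stratum GMCs whose shares differ by d have overall GMCs in the ratio 10^(g × d).

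**Step 2: how far shares differ by chance.** 95% limit for two groups: d = 1.96 × √(2p(1−p)/n).
- Central: 1.96 × √(0.48/50) = 0.192, about 19 points.
- Across six groups, simulation puts the average gap between highest and lowest share at 14 to 18 points (p = 20% to 70%).

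**Step 3: resulting ratio between identical groups.**

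| Case | d | Ratio |
|---|---|---|
| p = 20%, g = 0.5 | 0.157 | 10^0.078 = 1.20 |
| p = 40%, g = 1 | 0.192 | 10^0.192 = 1.56 |
| p = 50%, g = 1.5 | 0.196 | 10^0.294 = 1.97 |
| p = 40%, g = 1, pooled same-dose columns, n ≈ 100 | 0.136 | 10^0.136 = 1.37 |

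At a 10-fold gap, an 18-point difference gives 10^0.18 = 1.51, enough to cancel a true 1.5-fold advantage (1.5/1.51 = 0.99).

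**Step 4: precision in the central case.**
- Crude variance: (0.45² + 0.24 × 1²)/50 = 0.4425/50 = 0.00885. SE 0.0941; 95% CI ×/÷ 10^(1.96 × 0.0941) = 1.53.
- Standardised, fixed weights: 0.2025/50 × 1.02 = 0.00413, where the factor 1.02 is the post-stratification cost. SE 0.0643; CI ×/÷1.34. Variance gain 0.00885/0.00413 = 2.1.
- Counting uncertainty in a common share estimated from 300 participants: add 0.24/300 = 0.0008, giving 0.00493 and a gain of 1.8.
- Ratio of two groups: crude 10^(1.96 × √2 × 0.0941) = 1.82; standardised 10^(1.96 × √2 × 0.0643) = 1.51. With common weights, their uncertainty cancels here if the dose effect is the same in both strata.

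**Step 5: does CI width depend on the share?** With the same s and g, the crude factor is 1.33 at p = 0, 1.51 at 30%, 1.54 at 50% and 1.51 at 70%. The GMC and the CI limits move with the share; the width hardly changes between 30% and 70%.

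Fold increases are also means of logs, so Step 1 applies to them with their own gap, which is not sized here.

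**The case against.** The strongest reply is that the plan already supplies what a careful reader needs. Results by serostatus stand beside the overall ones (SAP 5.1.6, 5.4.3). Baseline serostatus is tabulated by schedule (SAP 5.8.4, 6.4), each geometric mean comes with its N, and seropositive adolescents get seropositive young-adult comparators (SAP 2). A standardised GMC could be rebuilt from those tables. This stands. It confines the point to the overall column and to the missing statement of which reading is the main one.

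A reader might infer that the overall comparison is biased or its CI invalid. The documents do not support that. Serostatus precedes randomisation, so imbalance between groups is chance, and the crude CI is correct for the enrolled mix. The central artefact of 1.56 lies inside the crude ratio factor of 1.82. The standardised interval is narrower because it removes a removable source of variation, not because the crude one is wrong.

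A reader might also infer that dose selection hangs on this column. SAP 3 says the choice rests primarily on safety and reactogenicity, SAP 5.9.1 says the selection guidelines will not be assessed in this study, and no rule uses the overall GMC. Immunogenicity is still considered (SAP 3, 5.9), so the column matters, but indirectly.

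Timing is a fair constraint too. SAP 2 already reports findings from the primary analysis, at which the sponsor is unblinded (SAP 5.9), so replacing a planned primary-endpoint display now would be hard to defend.

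**Conclusion.** The point holds as one of avoidable noise and unclear presentation. The overall GMC/GMT and fold increase follow each group's own seropositive share, and the plan leaves that variation in although baseline serostatus is collected and the SAP ranks it first among influences on response. For groups of 50, chance imbalance alone can give a GMC ratio of 1.2 to 1.97 between identical groups. Adjustment in the central case is worth a variance gain of about 2.1 for a single group, or 1.8 once uncertainty in the weights is counted. All of this rests on assumed SD, share and gap. The effect is modest at a 3-fold gap and becomes large from about 5- to 10-fold. The by-serostatus results are not affected.

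**What to change.** 1. State in SAP 5.4.3 that the by-serostatus results are the main reading of the primary immunogenicity endpoint.
2. For the final analysis, keep the crude overall figure and add beside it a GMC/GMT and fold increase standardised to one common serostatus mix, namely the seropositive share of all groups combined, or equivalently adjusted for baseline serostatus. Show the number positive and negative per group.
3. Label the added line as introduced after the primary analysis.
4. Limit it to the all-ages columns. With about 30% of 50 aged 16 to 17, a group has about 15 such participants, or about 6 seropositive at a 40% share, too few to standardise.
5. Leave seroresponse rates by serostatus with the planned exact intervals. If an overall standardised rate is wanted, use an interval that stays valid at 0% or 100%; one built from within-stratum variances gets zero width from a stratum at either extreme.

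The cost is some SAP wording, a few lines of code and one extra line per table. Participants with no baseline serostatus (SAP 5.8.4) drop out of the standardised line but stay in the crude one.
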